4.7.2.1 Infusion-Related Reactions

An IRR and its corresponding symptoms are collected on the dedicated eCRF page.

The symptom(s) of an IRR and the IRR itself may be of different intensities. Because other symptoms can be recorded as free text on the eCRF page, symptoms will be coded in the MedDRA and summarized by PTs.

For IRRs, the number and percentage of patients with at least one infusion reaction will be presented per infusion (patients with multiple events within an infusion will count only once). In addition, the total number of IRRs will be summarized (multiple events will be counted). The total and percentage of events (based on the total number of patients

with at least one IRR) by most extreme intensity will be summarized per infusion and per dose. The number of serious IRRs will also be presented.

For multiple events in a given patient, the most extreme intensity will be used and the total number of events of each intensity will be equal to the total number of patients with at least one IRR if there are no missing extreme intensities. The total number of IRRs experienced by each subject will be summarized across the treatment doses.

IRRs are recorded on the CRF by the time of the event, (i.e., occurring during the infusion, after completion of the infusion while patient is in the clinic, or within 24 hours of completion of the infusion and the patient is not in the clinic). The number of patients with at least one IRR, the total number of IRRs, and the intensity of the IRR will be presented by the time of event.

Additionally, similar tables will be presented by the premedication subgroup (methylprednisolone alone, methylprednisolone plus analgesic/antipyretics, methylprednisolone plus antihistaminics, or methylprednisolone plus analgesic/antipyretic and antihistaminics).

Symptoms of IRRs and symptoms of serious IRRs will be presented by infusion. Symptoms of IRRs that led to modification of study drug or symptoms of IRR that led to discontinuation of study drug will also be presented. Symptoms of IRR experienced by patients during an infusion, after the infusion, and after the patient leaves the clinic will also be presented.

AEs other than IRRs experienced by the patient within 24 hours of an infusion will be presented by infusion. AEs will be included if the onset date is on the day of an infusion or the following day. The onset date of the AE will be matched to the date of an infusion; onset dates will not be imputed.

The concomitant treatments for IRRs will be summarized.

4.7.2.2 Infections

Infections will be defined from the AE data using the MedDRA SOC of “Infections and infestations.” During Primary CSR, AEs reported as an infection by the investigator will also be included. Infections will be classified according to the pathogen type (e.g., bacterial, fungal, viral, parasitical, unknown, or other).

During Primary CSR, an infection has been defined as serious if the event is a SAE or if the non-serious infection was treated with an IV anti-infective. For subsequent reporting, an infection has been defined as serious if the event is a SAE.

A listing will be presented of non-serious infections treated with an IV anti-infective during primary CSR. The number of patients who experienced an infection will be summarized by SOC and PT and by intensity.

The number of infections experienced by more than 5% of patients will be summarized by SOC and PT.

The number of patients who experienced a serious infection will be summarized by SOC and PT.

Identified pathogen codes will not be summarized but will only be listed within the listings of infections and serious infections. Infections and serious infections will be summarized by pathogen types.

The time to the first serious infection per patient will be summarized by treatment.

The rate per 100 patient-years by treatment group (along with the 95% CI) will be calculated for infections and serious infections overall and by dose based on the number of patient-years observation for the specific dose.

For infections and serious infections, the incidence rate ratio will be calculated. For these analyses, the incidence rate ratio with 95% CI based on the Poisson distribution exact method will be presented.

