abnormalities in vital signs, ECGs, or laboratory parameters were observed in association with ocrelizumab treatment.

On review of the placebo-controlled, double-blinded, 24-week safety data, no imbalance in adverse events (or infection adverse events) or serious adverse events (or infection serious adverse events) between the placebo and the active ocrelizumab arms was observed. The rate of adverse events (or infection adverse events) and serious adverse events (or infection serious adverse events) did not increase in ocrelizumab-treated participants at Week 48 compared with Week 24. No trend toward an increased risk of adverse events (or infection adverse events) or serious adverse events (or infection serious adverse events) was found for ocrelizumab-treated participants with previous IFN treatment (for 6 months).

By the time all participants finished Week 48 of treatment, the incidence of infections and serious infections was 92.41/100 participant-years (PY) (95% CI: 76.59, 111.5) and 3.39/100 PY (95% CI: 1.27, 9.04) in participants exposed to low-dose ocrelizumab, including participants who switched from placebo or IFN β -1a. The incidence of infections and serious infections was 97.38/100 PY (95% CI: 74.76, 126.84) and 5.31/100 PY (95% CI: 1.71, 16.47) in those exposed to the high dose of ocrelizumab. The most common infections in ocrelizumab-treated participants included urinary tract infections, upper respiratory infections, and nasopharyngitis.

To date, in Study WA21493, after over 250 participant-years of exposure to ocrelizumab, no reports of opportunistic or fatal infections have been made.

Please refer to the Ocrelizumab Investigator's Brochure for more information.

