4.5.3 Exploratory Efficacy Endpoints

The MS guideline of the European Medicines Agency ([EMA, 26 March 2015](#)) suggests a number of primary and secondary efficacy outcome measures. On the basis of these recommendations, the following exploratory efficacy outcomes will be analyzed:

- MRI derived parameters: number of gadolinium-enhancing T1 lesions and number of new or enlarging T2 lesions. For the combined ECP and OLE periods, these parameters will be analyzed by scheduled visit as follows:
 - Negative binomial model adjusted by Geographical Region (US vs. ROW) and Age (≤ 45 , > 45 years) for the baseline visit.

- Negative binomial model adjusted by Baseline T1 Gd Lesion (present or not) or Baseline T2 lesion count, Geographical Region (US vs. ROW) and Age (≤ 45 , >45 years) for the post-baseline visits.
- If the negative binomial model doesn't converge due to small number of lesion counts, unadjusted rate and exact poisson CI will be presented.
- Cognitive impairment: change from baseline to Week 120 in the Paced Auditory Serial Addition Test (PASAT).
- Percent change from baseline to Week 120 in total brain volume, white matter volume and cortical gray matter brain volume and the percent change from Week 24 to Week 120 in white matter volume and grey matter brain volume. For all parameters, analyses will be extended to include data collected during the OLE period where percentage change from Week 24, baseline and OLE baseline until the last mature visit will be analyzed.

Additional exploratory outcomes that will be analyzed include the following:

- Proportion of patients with CDP at Week 120
- Functional impairment: change from baseline in EDSS score, and change from baseline in MSFCS. For both parameters, analyses will be extended to include data collected during the ECP and OLE periods. Change from baseline during ECP, change from baseline until the last mature visit during the combined ECP+OLE periods and change from OLE baseline until the last mature visit during the OLE period will be analyzed.
- The change in fatigue, as measured by the Modified Fatigue Impact Scale (MFIS) total score and subscale scores (Physical impact, Cognitive impact, and Psychological impact) from baseline to Week 120. Additional data from the OLE period will be descriptively analyzed.
- The change in quality of life, as measured by the SF-36v2 MCS score from baseline to Week 120. Additional data from the OLE period will be descriptively analyzed.

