The number of patients who experienced a related AE will be summarized by SOC and PT. AEs will be summarized by SOC and PT by intensity grade. Multiple occurrences of the same event within a patient will be counted once at the greatest intensity/highest grade for this PT. For AEs leading to death, the most extreme intensity will be overwritten by Grade 5 (death). Any AEs and the SOC overall rows of the summary table will count patients according to AEs by intensity (grade).

All patient deaths, regardless of treatment received, will be listed.

SAEs will be defined as all SAEs including serious MS relapses and serious IRRs. The number of patients who experienced an SAE will be summarized by SOC and PT. Related SAEs will be summarized by SOC and PT. Additionally, the most frequent SAEs ($\geq 1\%$) will be presented by PT.

A patient may experience an AE that leads to the discontinuation of his/her study treatment. Discontinuation of study treatment for an AE may not necessarily lead to discontinuation from the study because the patient can enter the SFU period of the protocol. Only AEs that led to the discontinuation of study treatment are of interest. Patients who withdraw early from the study because of AEs will be summarized under disposition. The number of patients who experienced an AE that led to discontinuation of study treatment will be summarized by SOC and PT. The number of patients who

experienced an AE that led to modification or interruption of study drug will be summarized by SOC and PT.

For each treatment group, the incidence count for each AE PT will be defined as the number of patients reporting at least one treatment emergent occurrence of the event. The incidence rate will be calculated as the incidence count divided by the total number of patients in the population. Each table will also present the overall number of patients experiencing at least one AE and the total number of AEs reported (multiple occurrences of the same AE in 1 patient will be counted only once).

The rate per 100 patient-years by treatment group (along with the 95% CI) will be calculated for specific events of interest such as all AEs, SAEs, infections and serious infections, opportunistic infections (OIs), and malignancies (see Section 4.7.2.2, Section 4.7.2.3 and Section 4.7.2.4, respectively).

- The number of AEs per 100 patient-years is calculated as:

Total number of AEs / Total number of patient-years \times 100

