- The 95% CI for the number of AEs per 100 patient-years is calculated as follows (Sahai and Kurshid 1993):

Exact lower 95% confidence limit = $\text{chisq}(p=0.025, df=2Y) / (2T)$

Exact upper 95% confidence limit = $\text{chisq}[p=0.975, df=2(Y+1)] / (2T)$

where Y is the total number of AEs, T is total number of patient-years at risk and $\text{chisq}(p,df)$ is the quantile of the upper tail probability of the X^2 distribution on df (degrees of freedom). This approach has the advantage of providing an estimate for the upper 95% confidence limit even when the total number of AEs is zero.

The rates per 100 patient-years will be summarized by treatment and dose and by treatment (including all doses).

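### Exact Poisson 95% limits for all AEs and all infections ignore clustering of events within patients, and are too narrow whenever it is present

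*SAP*

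**What the plan says.** SAP 4.7.2 (Adverse Events) defines the rate per 100 patient-years from "Total number of AEs / Total number of patient-years", multiplied by 100. It gives exact chi-square limits "where Y is the total number of AEs, T is total number of patient-years at risk". The rate with its 95% CI "will be calculated for specific events of interest such as all AEs, SAEs, infections and serious infections", and also for opportunistic infections and malignancies. Rates are reported by dose and over all doses.

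SAP 4.7.2.2 (Infections) repeats the rate and CI for infections and serious infections and adds the incidence rate ratio: "For these analyses, the incidence rate ratio with 95% CI based on the Poisson distribution exact method will be presented".

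No part of SAP 4.7 provides a dispersion term, a patient-level variance or another count model for these quantities. Elsewhere the SAP does: section 4.5.3 uses a negative binomial model for MRI lesion counts and falls back on exact Poisson limits only when that model fails because counts are small.

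Two further statements bear on the point. For the incidence tables, SAP 4.7.2 says that "multiple occurrences of the same AE in 1 patient will be counted only once"; it does not say whether this governs Y in the rate. SAP 4.7.2.2 also includes patient-level summaries: numbers of patients with an infection and with a serious infection, and "The time to the first serious infection per patient will be summarized by treatment".

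**The concern.** Exact Poisson limits on a pooled event count are valid if every patient has the same underlying rate and events within a patient are independent. If some patients are more susceptible, the variance of the total exceeds its mean and the limits are too close together.

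This matters little when almost nobody has two events. It matters when repeats are normal, as they are for all infections at the rate seen in the Phase II study (Protocol 2.1.4.1). The Protocol also gives reason to expect unequal susceptibility: section 4.1.5.3 reports fewer serious infections in patients aged 55 or less in the rituximab PPMS study, and section 7.3.1.1 describes an apparent association of serious infections with sustained immunoglobulin decrease.

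Infection is listed as an identified risk in Protocol 7.3.1.1. A reader will use the printed interval to judge how precisely the infection rate and the between-arm ratio are known. An interval labelled 95% that covers much less often overstates that precision, whichever way the estimate falls.

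**Working it through.** **The plan's own figures.** The SAP states no numerical interval here, so there is none to reproduce. The nearest are the Phase II intervals in Protocol 2.1.4.1. For low-dose infections, 92.41 (76.59, 111.5) per 100 patient-years matches rate × exp(±1.96/√Y) with Y = 109: 1.96/√109 = 0.188, giving 76.59 to 111.49, with 109/0.9241 = 117.95 patient-years. Low-dose serious infections, 3.39 (1.27, 9.04), back-solve to Y = 4 and 4/0.0339 = 118.0 patient-years. The two agree on exposure, so the Phase II intervals look like plain Poisson intervals on event counts. They carry no information about dispersion.

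**Inputs.**
- Patients: 732 enrolled (SAP 2.2), randomized 2:1, so 732 × 2/3 = 488 and 244.
- Follow-up: the minimum is 120 weeks (SAP 2), and 120 × 7/365.25 = 2.3 years. Assumption: uniform over 2.3 to 3.3 years, mean 2.8.
- Infection rate: 0.92 per patient-year (Protocol 2.1.4.1, low dose). Serious infections: 0.034.
- All-AE rate: not given. Assumption: 2.5 per patient-year.
- Dispersion k, with variance μ + kμ²: not given. Assumption: gamma frailty with variance 0.25 to 1.0, and 0 as reference.

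**Closed form.** The mean count per patient is μ = 0.92 × 2.8 = 2.58. The true standard error exceeds the Poisson one by √(1 + kμ), so a nominal 95% interval covers about 2Φ(1.96/√(1 + kμ)) − 1.

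**Simulation.** 4,000 trials per setting with true ratio 1 and every occurrence counted. Rate limits are χ²(0.025, 2Y)/2T and χ²(0.975, 2(Y+1))/2T with lower-tail quantiles. Ratio limits are the exact conditional binomial ones. The comparator is a patient-level robust interval for the ratio.

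| k | √(1 + kμ) | Closed-form coverage | Rate, simulated | Ratio, simulated | Robust/exact width |
|---|---|---|---|---|---|
| 0 | 1.00 | 95% | 95.2% | 95.9% | 0.99 |
| 0.25 | 1.28 | 87% | 88.1% | 87.9% | 1.27 |
| 0.5 | 1.51 | 81% | 80.9% | 79.8% | 1.49 |
| 1.0 | 1.89 | 70% | 70.4% | 70.2% | 1.87 |

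The robust interval covers 94% to 96% throughout. With follow-up fixed at 2.3 years, exact ratio coverage is 88.6%, 83.9% and 74.1% at k = 0.25, 0.5 and 1.0.

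**Where it is larger or smaller.**
- All AEs at the assumed 2.5 per patient-year: rate coverage 77.6%, 64.5% and 51.4% at k = 0.25, 0.5 and 1.0.
- Serious infections at 0.034: rate coverage 94.3% to 95.8% and ratio coverage 95.2% to 96.6% for k from 0 to 1.0. Even at k = 2 they are 92.9% and 94.1%.
- Infection rates within one 24-week dose: 24 × 7/365.25 = 0.46 years and μ = 0.92 × 0.46 = 0.42, so the inflation is √(1 + 0.25 × 0.42) = 1.05 to √(1 + 0.42) = 1.19. The problem lies mainly in the all-dose figures.

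**Is the range of k plausible?** At 0.9241 per patient-year over 96 weeks, μ = 0.9241 × 96 × 7/365.25 = 1.70. Poisson would put 1 − exp(−1.70) = 81.7% of patients with at least one infection. The rituximab PPMS study had 68.2% and 65.3% (Protocol 2.1.4.3). Solving 1 − (1 + kμ)^(−1/k) for these gives k of about 0.65 and 0.83. This combines the rate from one study with proportions from another, in different drugs and MS types, so it shows only that the assumed range is not extreme.

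**The case against.** The strongest reply has five parts.

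*Safety is descriptive.* SAP 4.7 says so, and SAP 4.5 ties hypothesis testing to the efficacy endpoints. This stands. A reader might infer that the trial has an inflated type I error for infection risk, because the ratio interval would exclude 1 too often under no difference. The documents plan no such test and attach no decision to that interval. A reader might also take the infection rate ratio to be the main comparative safety statistic; nothing in either document says this. What remains is that an interval labelled 95% should cover about 95%.

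*Patient-level summaries already exist.* They do, and repeat events do not distort them. But they do not correct the limits printed with the rates and the ratio, and the time-to-event summary covers serious infections only.

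*The counting rule may remove repeats.* If the once-per-patient rule in SAP 4.7.2 also governs Y, repeats of the same term drop out and the coverage figures above are too pessimistic. Different AEs or infections in one patient would still be pooled as independent. The SAP needs to say which count is used.

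*Exact limits were chosen for a reason.* SAP 4.7.2 notes that they give an upper limit even with no events. This stands for rare events. It would be tempting to extend the criticism to serious infections, opportunistic infections, malignancies and the lesion-count fallback, where "If the negative binomial model doesn't converge due to small number of lesion counts, unadjusted rate and exact poisson CI will be presented". The calculation does not support that for serious infections, and the same reasoning applies to other rare events. In the fallback, counts are small by definition, so a robust variance would be least reliable.

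*Consistency and timing.* The SAP's amendment rationale aligns the AE rate CI with the RMS studies, and SAP 2.3 lists the primary report as completed. This supports keeping the exact interval visible, and labelling any re-analysis of the blinded period as added after unblinding. It does not make the limits right.

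**Conclusion.** The point holds for all AEs and all infections: the exact Poisson limits for their rates, and for the infection rate ratio, leave out between-patient heterogeneity and are too narrow whenever events cluster within patients. Under the stated assumptions, coverage for infections is about 88% at dispersion 0.25 and about 70% at 1.0. The direction is secure. The size is not, because the dispersion is assumed and every occurrence is taken to count; at zero dispersion the intervals are correct.

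The point does not reach any confirmatory conclusion, and it is negligible for serious infections at the planning rate. The ratio figures concern the randomized comparison. In the open-label phase all patients receive ocrelizumab, so there only the single-arm rates are at issue.

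**What to change.** In SAP 4.7.2 and 4.7.2.2, for all AEs and all infections only:

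- Derive the 95% CI for the rate, and for the infection rate ratio, from a negative binomial model or from a Poisson model with patient-level robust variance, with log patient-years as offset.
- State whether Y counts repeat occurrences of the same AE in a patient.
- Show the exact Poisson interval alongside if comparability with the RMS studies is wanted.

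Keep exact Poisson limits for serious infections, opportunistic infections, malignancies, sparse or zero-count cells (including sparse by-dose cells) and the lesion-count fallback in SAP 4.5.3.

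The cost is SAP wording, one extra model per table, and wider intervals: about 1.3 to 1.9 times as wide for the infection rate ratio over the assumed dispersion range, and essentially unchanged if there is no dispersion. SAP 2.3 lists the final report as planned, so the change can be made there.

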4.7.2.3 Opportunistic Infections

Opportunistic infections (OIs) will be defined using the Ocrelizumab specific MedDRA Term Selection (MTS) basket of “Opportunistic infections.”

The number of patients who experienced an OI will be summarized by SOC and PT.

The rate per 100 patient-years by treatment group (along with the 95% CI) will be calculated for OIs overall.

4.7.2.4 Malignancies

Malignancy and pre-malignancy AEs will be identified using the standard MedDRA query (SMQ) of “Malignant tumours (narrow)” and “Pre-malignant disorders,” respectively.

The number of patients with a malignancy will be summarized by SOC and PT. The pre-malignancy AEs will be listed.

The rate per 100 patient-years by treatment group (along with the 95% CI) will be calculated for malignancies.

4.7.2.5 Multiple Sclerosis Relapses

MS relapses will include all events recorded on the AE CRF pages that are classified as MS relapse.

Information related to a protocol defined relapse will be captured on a clinical relapse event CRF page. If the following criteria are satisfied, the clinical relapse will qualify as a protocol defined relapse:

- Check box labeled “Did symptoms persist for >24 hours and were not attributable...” on the clinical MS relapse event CRF page is checked.
- Increase in EDSS from a visit occurring at (or soon after) the date of onset of relapse of ≥ 0.5 compared with the previous EDSS; or for selected FS domains involved in the relapse event (pyramidal, ambulation, cerebellar, brainstem, sensory, or converted visual), a ≥ 2 point increase in one appropriate FS domain or a ≥ 1 point increase in two or more appropriate FS domains.
- No protocol defined relapse within 30 days before the date of onset of the clinical relapse.

For protocol defined relapses and clinically reported relapses (i.e., patients who experience any relapse), the number and percentage of patients experiencing an event will be summarized.

Clinical relapse will be considered an SAE when the relapse results in hospitalization for any reason other than routine treatment of the relapse (e.g., for a treatment course beyond the standard treatment described or when hospitalization is prolonged). These events will be listed and summarized.

4.7.2.6 Pregnancies

Pregnancy information will be summarized.

4.7.3 Magnetic Resonance Imaging Data

Non-MS pathology reported by the local safety radiologist on the CRF will be summarized by treatment group.

4.7.4 Laboratory Data General Laboratory Evaluations

Abnormal laboratory outcomes will be reported. A summary of the number and percentage of patients with abnormal laboratory outcomes, along with each grade by laboratory parameter, will be summarized by treatment group for all laboratory assessments.

The absolute values and changes from baseline at each visit will be summarized for all laboratory assessments.

For the liver laboratory parameters, the number and percentage of patients with an elevated post-baseline AST or ALT level will be summarized by treatment.

CD19

The median CD19 cell count will be displayed graphically over time from the first infusion of study drug. Absolute CD19 counts and percent changes from baseline in the CD19 count will be summarized over time.

Immunoglobulins

The median immunoglobulin levels (IgA, IgG, IgM, and total Ig) will be displayed graphically over time from the first infusion of study drug. Absolute values, changes from baseline, and percent changes from baseline will be summarized over time. At each timepoint, the number and percentage of patients with immunoglobulin levels lower than the lower limit of normal will be presented.

Antibody Titers

If data are available, antibody titers for mumps, rubella, varicella, and *Streptococcus pneumoniae* will be summarized for the number and percentages of patients with a positive level by visit.

Anti-Drug Antibodies

ADAs, also called human anti-human antibodies, will be summarized over the blinded treatment period by treatment group. The baseline prevalence and post-baseline incidence of ADAs will be displayed. The number of patients with treatment-induced ADA will also be displayed. A table that summarizes ocrelizumab serum concentrations ($\mu\text{g/mL}$) at timepoints where ADA samples were collected and analyzed will be presented. A listing by treatment of antiocrelizumab antibody data will be presented for patients with at least one ADA sample.

HBV DNA

HBV DNA in patient core HBV antibody positive at screening will be listed.

